The efficacy of extended-release (ER) levomilnacipran has been established for major depressive disorder (MDD) in doses ranging from 40 mg/day to 120 mg/day (Sambunaris et al, 2014; Asnis et al, 2013). Levomilnacipran is the most noradrenergically active of the SNRI class of antidepressant drugs. Levomilnacipran was found to have twofold greater potency for norepinephrine relative to serotonin reuptake inhibition, and 17 and 27 times higher selectivity for norepinephrine reuptake inhibition compared with venlafaxine and duloxetine, respectively (Auclair et al, 2013).

Cognitive dysfunction in MDD is common and associated with greater impairment in functioning and quality of life. Given the similarities in mechanisms of action, it is possible for levomilnacipran to have beneficial effects on neurocognition. Apathy is considered a disorder of motivation and can occur in neuropsychiatric syndromes as well as depression. It is associated with neurocognitive disturbances and functional impairment. It remains understudied in depression.

Augmentation by adjunctive atypical antipsychotics is recommended as one of the clinical strategies on par with antidepressant switch in the APA guidelines to treat MDD. Quetiapine (extended release) is an atypical antipsychotic approved as adjunct to antidepressants for treatment of MDD in doses between 150-300 mg/day and has been extensively used in clinical practice.

Needs assessment: There is a significant unmet clinical need in terms of patients with MDD who show inadequate response and remission with SSRI treatment. Scientific evidence that guides appropriate treatment strategies in terms of further steps of switching or augmentation of medications will improve clinical care in patients with MDD who do not show adequate response to SSRIs.

II. STUDY OBJECTIVE(S):

Primary:

1. To compare the efficacy and tolerability of switching to levomilnacipran ER (40-120 mg/d) versus augmentation with quetiapine 150-300 mg/day to the patients' existing treatment for patients with inadequate relief on generic SSRIs in patients with MDD.

Secondary:

1. To examine the response and remission rates following the switch from generic SSRI to levomilnacipran ER and augmentation with quetiapine.
2. To examine changes in neurocognitive and apathy measures after switching from SSRI to levomilnacipran and after augmentation with quetiapine in MDD

III. STUDY DESIGN and PLAN:

Methodology:

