 - Weekly phone calls will include a Symptom Checklist, consistent with symptoms of Major Depression, suicidal risk and adverse events, which the Study Coordinator will review with the subject. Any potential concerns will be reviewed with the subject. Any potential concerns will be discussed with the PI and appropriate interventions for subject safety will be planned. The same symptom checklist and monitoring plan for the subjects will be used at the Duke and the non-Duke site.
- Assess all applicable inclusion and exclusion criteria

- Administer the C-SSRS, MADRS, ASEX, HAM-A, DSST, CGI-S, RVLTL, AES, Spontaneous Reported AEs and Sheehan Disability
- Assess for and record AEs and concomitant medications
- Dispense study medication

The following activities and/or assessments will be performed at Weeks 1 through Weeks 6:

- Assess for and record AEs and concomitant medications
- Administer the C-SSRS, MADRS, ASEX, HAM-A, DSST, CGI-S, RVLTL, AES, Spontaneous Reported AEs and Sheehan Disability
- Collect study medication and review medication compliance
- Dispense study medication

The following activities and/or assessments will be performed at Week 8: End of Study or Early Termination:

- Assess for and record AEs and concomitant medications
- Collect study medication and review medication compliance
- Record vital signs (temperature, heart rate, supine and orthostatic blood pressure), and body weight
- Collect blood and urine samples for evaluation of standard laboratory safety tests
- Administer the C-SSRS, MADRS, ASEX, HAM-A, DSST, CGI-S, RVLTL, AES, Spontaneous Reported AEs and Sheehan Disability
- Perform a 12-lead ECG

The following activities and/or assessments will be performed at the Week 9/ Safety Follow-Up Visit:

- Assess for and record AEs and concomitant medications
- Administer the C-SSRS, Spontaneous Reported AEs and the DSST

After all study assessments has been completed or if the participant completes an early term visit, the participants will be referred back to their outpatient treating physician for

psychiatric care. Participants who are uninsured will be referred to Lincoln Community Health Center or Durham Access. Results of the subject's participation will not be available to the subject before they return to their treating doctor.

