Using Cohen's d effect size to determine sample size, in Cohen's standard text on statistical power (Cohen, 1988), using the NICE definition of a $d=0.5$ or larger, we obtain an estimated sample size (given a two-sided $\alpha = 0.05$ and $1 - \text{Beta} = 0.800$) of $n= 30$ per arm or 60 for the study. A power analysis was also conducted based on an effect size estimate derived from the drug-placebo difference in primary outcome of MADRS scores in published levomilnacipran trials (Citrome, 2013). The summary of Least square mean change between drug and placebo at 95% CI was -4.9 ($p<.0001$). With a two-tailed $\alpha= 0.05$, a sample size of $n= 60$ provides a power of 0.80.

B. Randomization Method

Randomization will occur with randomly generated computer lists held at the Duke site. This group will assign subjects according to a computer-generated the randomization sequence (without blocking or stratification) for each site. After the study coordinator determines eligibility, the participant will be randomized to one of two different arms. Drug capsules will be placed in standard medicine bottles. Each bottle will be dispensed individually by the study coordinator at the appropriate visit. Rater unblinding will be done at the end of the study after data lock. In case of any AEs or SAEs or other emergencies that require the blind to be broken, the pharmacy will have a 24-hour on call support service.

Power analysis was performed using an internet based software program. The results showed that a sample size of $n=60$ ($n=20$ in each of the 3 groups) could detect a strong effect with $\alpha = .05$, unless the true mean difference is quite minimal.

C. Plan of Data analysis

Subjects will be defined as able to be evaluated by two methods. The primary method will be an intent-to-treat analysis, including those who discontinue drug due to lack of efficacy or due to side effects. The secondary method will be completer analysis. The intent-to-treat (ITT) group will include randomly assigned patients receiving study drug with a post baseline efficacy assessment. The safety population will comprise all patients receiving study drug with a post baseline safety assessment.

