Primary efficacy analysis will be conducted in the ITT population using the last-observation-carried-forward (LOCF) method. Treatment group comparisons will base on changes in MADRS from baseline to week 8/end of treatment from repeated measures ANOVA or analysis-of-covariance (ANCOVA) model containing treatment site, gender and baseline MADRS score included as a covariate.

Secondary efficacy analysis: Repeated measures ANOVA or ANCOVA models will be used to analyze change from baseline in secondary measures. Response and remission rates at end of treatment will be compared using the Cochran-Mantel- Haenszel test. No formal hypothesis testing will be performed on safety data. Safety outcomes will be summarized by treatment group and study visit (observed cases) using descriptive statistics. Any clinically significant findings among patients who terminated early will be discussed separately. All analyses will be conducted using SAS Version 9.1.3 (SAS Institute, Inc.; Cary, North Carolina). Statistical comparisons of efficacy outcomes will be 2-sided and considered significant at $P < .05$. Comparisons for secondary endpoints will be not adjusted for multiplicity.

D. Definition of Evaluable Subject (Safety and Efficacy)

Subjects will be defined as able to be evaluated by two methods. The primary method will be an intent-to-treat analysis, including those who discontinue drug due to lack of efficacy or due to side effects. The secondary method will be completer analysis.

XI: ETHICAL AND REGULATORY CONSIDERATIONS

A. Institutional Committee Approval

Duke University Health Systems Institutional Review Board (DUHS IRB) will need to approve the protocol at the Duke site. [name] site will use an external IRB (e.g. Copernicus, Western) and provide Duke with a copy of its approval.

B. Informed Consent

Participation in this study is voluntary and at no cost to the subjects. All potential participants interested in this study must be thoroughly informed of the details of the study. Prior to study participation in this trial, each subject will have an opportunity to ask questions and will sign an approved informed consent form. The signed consent forms will be filed with the investigator's copies of the Case Report Forms for each subject and a copy provided to the subject. Any subject may voluntarily withdraw from the study at any time without prejudicing treatment.

C. Document Storage and Retention

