All data will be analyzed by the Duke site. The PI and Co-Is are solely responsible for data analysis, interpretation of results, presentation and publication of data produced by this study. The results of this study will be presented at national Conferences (APA, NCDEU) and published in peer reviewed journals (Journal of Clinical Psychiatry).

XII: PUBLICATION PLAN:

Presented at APA Annual meeting 2017, NCDEU annual meeting 2017 and article submitted to Journal of Clinical Psychiatry end 2016.

XIV. SCHEDULE OF EVENTS:
STUDY VISIT SCHEDULE

Test	Week -4 Screening	Week 0: Randomization/ Baseline	Week 1	Week 2	Week 3	Week 4	Week 6	Week 8: End of Study or ET	Week 9: Safety Follow- Up
Informed Consent	X								
Eligibility Criteria	X	X							
Demographic Data	X								
Medical/Surgical History	X								
Physical Exam	X							X	
Vital Signs	X							X	
Blood Samples & Laboratory tests	X							X	
Urine Samples Collect.	X							X	
ECG	X							X	
Psychiatric History/MINI	X								
Prior/concomitant meds	X	X	X	X	X	X	X	X	X
Washout instructions	X	X							
MADRS	X	X	X	X	X	X	X	X	
Columbia Suicide Severity Rating Scale	X	X	X	X	X	X	X	X	X
ASEX	X	X	X	X	X	X	X	X	
HAM-A	X	X	X	X	X	X	X	X	
HAM-D	X								
RVLT	X	X	X	X	X	X	X	X	
Spontaneous Reported AEs	X	X	X	X	X	X	X	X	X
DSST	X	X	X	X	X	X	X	X	
Sheehan Disability	X	X	X	X	X	X	X	X	
CGI-I and CGI-S	X	X	X	X	X	X	X	X	
Adverse event reporting	X	X	X	X	X	X	X	X	X
Drug Dispense/Account/Adjust		X	X	X	X	X	X	X

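### The safety plan specifies only by-visit observed-case summaries and a separate discussion of early leavers, so no by-arm table of patients ever affected or stopping for adverse events is promised, and early-termination records have no assigned analysis visit

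*Combined protocol and SAP*

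**What the plan says.** Section II makes tolerability part of the primary comparison: "To compare the efficacy and tolerability of switching to levomilnacipran ER" against augmentation with quetiapine.

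Section VII (Statistical Evaluation), C, gives the whole of the safety analysis. On testing it says: "No formal hypothesis testing will be performed on safety data". The rule for the tables is: "Safety outcomes will be summarized by treatment group and study visit (observed cases) using descriptive statistics". For those who leave: "Any clinically significant findings among patients who terminated early will be discussed separately". No criterion for clinical significance is given. The same section defines the analysis set: "The safety population will comprise all patients receiving study drug with a post baseline safety assessment".

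Section VII (Clinical Assessments), under Safety/Tolerability, names the reasons why patients drop out as one of the tolerability measures, and requires every spontaneously reported or observed adverse event to be recorded. The section on study discontinuation lists side effects, at the investigator's discretion, as a ground for leaving.

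On visits, Section V.C reads "The following activities and/or assessments will be performed at Week 8: End of Study or Early Termination", and the schedule in Section XIV has one column headed "Week 8: End of Study or ET". Neither section, nor the analysis section, says which analysis visit an ET record belongs to.

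**The concern.** A patient who stops because of a side effect is missing from the observed cases at every later visit, in numerator and denominator alike. The by-visit percentage then describes those who tolerated the drug well enough to stay. Equal dropout cannot be assumed: one arm tapers the SSRI and switches, while the other adds a drug to unchanged treatment.

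The plan does say how leavers enter the efficacy analysis (intent-to-treat with last observation carried forward). For safety there is no equivalent. Followed as written, it yields no table giving the share of treated patients in each arm who had a given event, or who stopped because of one. By-visit tables cannot be added up to supply it, because one patient may appear at several visits.

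A second gap concerns measures taken rarely. Vital signs, laboratory tests and ECG are scheduled only at screening and at Week 8/ET, and Section V.C lists body weight at the same two points. For these, the ET record is a leaver's only scheduled post-baseline value. Without a rule, it is either dropped from Week 8 or pooled with values taken after full exposure.

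**Working it through.** The documents give no adverse event rate and no dropout rate, so there is no stated figure to reproduce. The only input from the plan is 30 patients per arm (Section IV.A). All other counts below are assumptions that show how the mechanism works.

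**Step 1. Event counts.** Assume all 30 per arm are in the safety population, leavers go before Week 8, the event persists once it occurs, and no one who stays had an earlier, resolved event.

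- Arm A: 9 leave, 6 of them with the event; 4 of the remaining 30 − 9 = 21 have it at Week 8.
- Arm B: 3 leave, 1 of them with the event; 5 of the remaining 30 − 3 = 27 have it at Week 8.
- Week 8 observed cases, ET records excluded: 4/21 = 19.0% v 5/27 = 18.5%, a gap of 0.5 points.
- Ever affected: (6 + 4)/30 = 33.3% v (1 + 5)/30 = 20.0%, a gap of 13.3 points.
- Week 8 with ET records included and the event still present at exit: again 10/30 = 33.3% v 6/30 = 20.0%, so nothing is masked.

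**Step 2. Other assumed counts.** Here only affected patients leave. Week 8 observed = (affected − leavers)/(30 − leavers), with ET records excluded.

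| Ever affected, A v B | Left, A v B | Week 8 observed | Gap (points) | Ever affected, % | Gap (points) |
|---|---|---|---|---|---|
| 12 v 6 | 8 v 1 | 4/22 (18.2%) v 5/29 (17.2%) | 0.9 | 40.0 v 20.0 | 20.0 |
| 12 v 6 | 6 v 0 | 6/24 (25.0%) v 6/30 (20.0%) | 5.0 | 40.0 v 20.0 | 20.0 |
| 9 v 4 | 6 v 1 | 3/24 (12.5%) v 3/29 (10.3%) | 2.2 | 30.0 v 13.3 | 16.7 |
| 10 v 5 | 6 v 1 | 4/24 (16.7%) v 4/29 (13.8%) | 2.9 | 33.3 v 16.7 | 16.7 |
| 12 v 6 | 9 v 3 | 3/21 (14.3%) v 3/27 (11.1%) | 3.2 | 40.0 v 20.0 | 20.0 |

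Every set assumes that the arm with more affected patients also loses more of them. With no dropout, and under the persistence assumption, the two summaries agree.

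**Step 3. Mixed exposure.** Suppose instead that ET values are pooled as Week 8. Assume a steady change of 0.3 units per week and L of 30 patients leaving at Week 2. The pooled mean is [L × 2 × 0.3 + (30 − L) × 8 × 0.3]/30.

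- L = 0: 2.40, the full-exposure value.
- L = 3: (1.8 + 64.8)/30 = 2.22.
- L = 6: (3.6 + 57.6)/30 = 2.04.
- L = 9: (5.4 + 50.4)/30 = 1.86.

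The effects in Steps 1 and 3 are alternatives for a given table. Leaving ET records out risks hiding events; putting them in without regard to time on drug dilutes changes that build up.

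**The case against.** The strongest reply is that the information will exist and much of it will be visible. All adverse events are recorded. Leavers with a post-baseline safety assessment remain in the safety population. Visits at Weeks 1, 2, 3, 4 and 6 would show events reported before exit, and the shrinking denominators (21 v 27 in the example) would reveal unequal loss. Dropout reasons are a listed tolerability measure, and a summary of safety outcomes by treatment group could naturally include them. The separate discussion of leavers may be an added narrative, not a removal from the tables. All of this stands and limits the point. It does not close it, because the analysis section commits to neither per-patient incidence nor discontinuations by arm. A falling denominator shows that patients left, not why.

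A reader might go further and infer that leavers' last values are filed under Week 8. The documents do not say so: the shared heading and schedule column govern which procedures are done, not how records are analysed. That inference would also undo the masking example, since including ET records restores 33% v 20% when the event is still present.

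It is also fair that the counts are chosen, and that the example sets Week 8 prevalence against a cumulative count. Hence the stated assumptions and the range. ASEX is collected at every visit from baseline to Week 8, so the sparse-measurement problem does not extend to it.

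**Conclusion.** The point holds as a defect in how the safety summary is specified. With a tolerability comparison in the primary objective, the plan's only committed safety tables are by visit on observed cases, and these can understate a difference at later visits. Under the assumed counts, gaps of 13 to 20 points in patients ever affected shrink to between 0.5 and 5 points at Week 8. This requires unequal loss of affected patients, events that persist, and ET records left out of the table. Where ET records are included and the event is still present, the masking is absent.

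The missing rule for ET records is a separate, smaller gap. If they are pooled as Week 8, an assumed change of 0.3 units per week with 6 of 30 leaving at Week 2 gives a mean of 2.04 instead of 2.40.

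The documents do not support the conclusion that early leavers' safety data are hidden, or that one arm will in fact look better than it should: no event or dropout rates are given.

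**What to change.** In Section VII (Statistical Evaluation), C:

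1. Make the main adverse event summary the number and percentage of safety-population patients per arm with each event at least once, from first dose to last safety contact, leavers included.
2. Tabulate discontinuations by reason and arm, with adverse events as a named reason, and give time to discontinuation.
3. State that ET values are recorded by actual study day. For weight, vital signs, laboratory tests and ECG, show change to the last on-drug value with days on drug, beside the Week 8 completers.

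Keep the by-visit observed-case tables and the discussion of early leavers as additions. The cost is a short change of wording and two or three extra tables. No new data, visits or patients are needed.

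### The only second analysis of MADRS change is an undefined completer analysis, which leaves out the patients whose Week 8 values LOCF fills in and so cannot test the LOCF assumption

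*Combined protocol and SAP*

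**What the plan says.** Statistical Evaluation, section C (Plan of Data analysis), sets the primary analysis: "Primary efficacy analysis will be conducted in the ITT population using the last-observation-carried-forward (LOCF) method". The analysis set is defined there too: "The intent-to-treat (ITT) group will include randomly assigned patients receiving study drug with a post baseline efficacy assessment". Sections C and D both say that patients who stop stay in the primary method: "The primary method will be an intent-to-treat analysis, including those who discontinue drug due to lack of efficacy or due to side effects". Both then add the second method: "The secondary method will be completer analysis". Neither section says what a completer is.

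No other analysis of MADRS change under a different missing-data assumption is named. Repeated measures ANOVA or ANCOVA appears as an open choice of primary model, not as a second analysis.

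Two other places govern who leaves. The end of section V.C terminates patients whose MADRS worsens to a clinically significant degree at two visits running, or whose C-SSRS worsens at two visits running. Study Discontinuation/Termination, under Additional Information Regarding Study Conduct, adds adverse events (item 3) and clinical worsening (item 4).

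For safety, section C gives a separate set: "The safety population will comprise all patients receiving study drug with a post baseline safety assessment". It also says: "Safety outcomes will be summarized by treatment group and study visit (observed cases) using descriptive statistics". The heading of section D nevertheless names both safety and efficacy.

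**The concern.** LOCF assumes that a patient's last MADRS score stands in for the Week 8 score. A useful second analysis keeps those patients and changes that assumption. A completer analysis drops them, so the assumption is set aside and not examined.

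Completion is also decided after randomisation, and the protocol's own rules tie it to worsening and tolerability. The arms may well lose patients for different reasons. One tapers the SSRI and switches drug; the other keeps the antidepressant and adds quetiapine (section V.B). The completers of the two arms need not be comparable, and a difference between them mixes drug effect with selection.

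At stake is how the result is read. Agreement between the two analyses could be taken as support when both are biased the same way. Disagreement could cast doubt on a sound primary result.

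**Working it through.** **Step 1: the passages side by side.** The plan gives no dropout rate and no figure for this point, so there is nothing of its own to reproduce.

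| Question | Primary method | Second method |
|---|---|---|
| Patients who stop for lack of efficacy or side effects | kept | dropped, on the ordinary meaning of completer |
| Their Week 8 MADRS | last value carried forward | not used |
| Treated patients with no post-baseline efficacy assessment | excluded | excluded |

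The two methods differ exactly in the patients for whom LOCF acts, and no analysis gives those patients a different plausible value.

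**Step 2: size of completer bias (illustration).** The dropout rates, the links and the SD are all assumed. SD 9.8 equals 4.9 / 0.5, which joins two separate power statements in section A; the documents give no SD.

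Let Z be the standardised Week 8 outcome, higher meaning worse, with the same standard normal distribution in both arms. The chance of dropout is 1 / (1 + exp(−(a + bZ))), with a set to give the stated rate. The completer bias is SD × [E(Z | stay, arm 1) − E(Z | stay, arm 2)]. By numerical integration:

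| Dropout, arm 1 v arm 2 | Link b, arm 1 / arm 2 | Completer mean of Z | Bias at SD 9.8 (absolute) |
|---|---|---|---|
| 30% v 15% | 0.5 / 0.5 | −0.143 / −0.073 | 0.7 |
| 30% v 15% | 1 / 1 | −0.253 / −0.133 | 1.2 |
| 30% v 15% | 1 / 0 | −0.253 / 0 | 2.5 |
| 20% v 20% | 1 / 0 | −0.173 / 0 | 1.7 |
| 20% v 20% | 1 / 1 | −0.173 / −0.173 | 0 |

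For example, 9.8 × 0.253 = 2.5. The bias favours the arm that loses more of its poor responders. At SD 8 the first four rows become 0.6, 1.0, 2.0 and 1.4. A completer t-test from 30 randomised per arm has false-positive rates of about 5.7%, 7.1% and 14% in the first three rows, and about 5% in the last.

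**Step 3: completers against LOCF (illustration).** A second simulation, with 400,000 patients per arm, has no true Week 8 difference. Each patient's true Week 8 change is normal with mean −12 and SD 7. The value at week v is that change × √(v/8), plus noise of SD 5, so the total SD at Week 8 is √(49 + 25) = 8.6. Arm A loses its poorest responders at varying visits. Arm B loses patients at random, last seen at week 1 or 2. Differences are A minus B, and negative values falsely favour A.

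| Dropout A / B | Completer difference | LOCF difference |
|---|---|---|
| 10% / 10% | −1.2 | −0.7 |
| 20% / 20% | −2.0 | −1.0 |
| 30% / 30% | −2.8 | −1.4 |
| 10% / 30% | −1.1 | −2.0 |
| 30% / 10% | −2.8 | about −0.1 |

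In the fourth row both analyses point to the same false difference, so the completers appear to confirm it. In the last row LOCF is nearly unbiased and the completers contradict it.

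**Step 4: precision.** With 10%, 20%, 30% or 40% dropout, 27, 24, 21 or 18 completers per arm remain. Two-sample t-test power at d = 0.5 is then 0.44, 0.40, 0.35 or 0.31. A non-significant completer result would say little either way.

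**The case against.** The strongest reply is that the plan never calls the completer analysis a robustness check. It is a labelled second way of defining evaluable subjects. The primary analysis keeps "including those who discontinue drug due to lack of efficacy or due to side effects" types of patient, so the primary inference does not rest on completers, and reporting completers second is not an error in itself. This stands. The point is therefore an omission: nothing in the plan examines LOCF, and the one analysis placed beside it cannot do so.

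The size is also open to challenge. The SD is assumed, and equal dropout with the same link in both arms gives no bias. Two of the three false-positive rates at 30% v 15% are close to 5%. All of this stands, which is why the figures are given only as illustrations.

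The remedy is one of several. A mixed model on observed visits with reference-based imputation would also serve. What matters is that stopped patients are kept and the assumption about them is varied.

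A reader might infer from the heading of section D that completers are also the second method for safety, so that patients who stop for side effects drop out of the safety tables. The documents do not support that. The safety population does not require completion, and section C discusses clinically significant findings in early terminators separately. The Safety/Tolerability section includes reasons for dropout among its assessments. No completer safety analysis is planned.

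**Conclusion.** The point holds for efficacy. The plan offers LOCF and an undefined completer analysis for MADRS change, and the second cannot test the assumption behind the first. This follows from the text alone, given the ordinary meaning of completer, and does not depend on the simulations.

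Under the stated assumptions, completer bias runs from about 0 to 2.5 points, against the 4.9-point drug-placebo difference cited in the power section. A reader might take these biases or false-positive rates as properties of the trial's primary test. They are not: Step 2 describes only the completer analysis, and the LOCF column in Step 3 comes from one assumed dropout pattern.

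The change is a cheap improvement that should be made before unblinding. On safety, all that remains is a heading that does not match section C.

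**What to change.** - In Statistical Evaluation C and D, name as the sensitivity analysis of the primary outcome a multiple imputation of missing Week 8 MADRS, by arm, from all observed visits. The schedule already collects MADRS at Weeks 0, 1, 2, 3, 4, 6 and 8. With about 30 patients per arm the imputation model should be kept simple.
- Add fixed penalties to the imputed values of patients who stopped for lack of efficacy or side effects, for example 0, 2, 4 and 6 points, varied separately by arm. Report where the conclusion changes.
- State whether this analysis also covers randomised patients with no post-baseline efficacy assessment, whom both present methods omit.
- Define completer, and keep the completer results as descriptive.
- Reconcile the heading of section D with the safety population in section C, so that safety plainly uses that population.

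The cost is SAP wording and some extra programming, with no new visits, patients or data. The small downside is that the supporting result is reported over a range of assumptions and not as one P value.
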